^a Pre-treatment counts averages of at least 2 measurements (not influenced by transfusions, ie, no RBC transfusions for 2 weeks and no platelet transfusions for 1 week) ≥ 1 week apart (modification).

[figure not shown]
^b Modification to IWG (2000) response criteria.

^c In the absence of another explanation, such as acute infection, repeated courses of chemotherapy (modification), gastrointestinal bleeding, hemolysis, and so forth. It is recommended that the 2 kinds of erythroid and platelet responses be reported overall as well as by the individual response pattern.

[figure not shown]
Note: Deletions to the IWG response criteria are not shown. To convert hemoglobin levels from grams per deciliter to grams per liter, multiply grams per deciliter by 10.

Source: Cheson BD, Greenberg PL, Bennett JM, Lowenberg B, Wijermans PW, Nimer SD et al. Clinical application and proposal for modification of the International Working Group (IWG) response criteria in myelodysplasia. *Blood* 2006; 108 (2): 419-25.

[figure not shown]

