8.2. Baseline Disease Characteristics

Baseline disease characteristics includes following variables:

- MDS World Health Organization (WHO) 2008 classification,
- Eastern Cooperative Oncology Group (ECOG) performance status (0 – 1, 2),
- Time since initial diagnosis (defined as the number of months from the date of initial diagnosis to the date of randomization),
- IPSS score classification ([Greenberg, 1997, Appendix C](#)),
- Baseline platelet transfusion status (Dependent, Independent),
- Average baseline RBC transfusion requirements (units per 28 days) and category (≤ 4 units per 28 days, > 4 units per 28 days),
- Bone marrow blasts baseline values and category ($< 5\%$, $\geq 5\%$),
- Hgb (g/dL) values,
- Platelet count ($10^9/L$) values,
- Absolute neutrophil count ($10^9/L$) values,
- White blood cell count ($10^9/L$) values,

- Transferrin saturation baseline values (%) values.

Subjects will be considered platelet transfusion dependent at baseline if they have received ≥ 2 platelet transfusions during the 56 days immediately preceding randomization and had no consecutive 28-day period during which no platelet transfusions were administered.

The average number of units (in 28 days) of baseline RBC transfusions is determined by the following rules:

If the subject was randomized under the original protocol and protocol amendment 1, the average number of units per 28 days = sum of RBC transfusion units during the 84-day interval prior to the randomization date / 84 days * 28 days.

- If the subject was randomized under protocol amendment 2, the average number of units per 28 days = sum of RBC transfusion units during the 56-day interval prior to the randomization date / 56 days * 28 days.
- RBC transfusion and whole blood transfusion during the above specified period will be included. For whole blood transfusion, the number of units collected in the CRF will be used to calculate the RBC transfusions required units.

To eliminate the impact of transfusion, the baseline values for Hgb will be determined by following steps:

Step 1: Apply the “7-day rule” on all Hgb values from the Central lab which are collected on or prior to Cycle 1 Day 1. Use the lowest value among the Hgb values which are collected after >7 days of a RBC/whole blood transfusion or collected on the same of the transfusion as the baseline value.

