Step 2: For subjects who don’t have baseline value from Step 1, apply the “7/3-day rule”. Use the lowest value among the Hgb values from the Central lab which are collected within 7 days after a RBC/whole blood transfusion and within 3 days before another transfusion as the baseline value. The rationale is that the Hgb value within 7 days from the first transfusion was only somewhat influenced by that transfusion.

Step 3: For subjects who don’t have baseline values from Steps 1 and 2, use the lowest value among all Hgb values from the Central lab which are collected on or prior to Cycle 1 Day 1.

The baseline values for platelet count will be determined similarly to eliminate the impact of platelet transfusion.

For absolute neutrophil count, white blood cell count and bone marrow blasts, the baseline values will be determined by selecting the last non-missing value from the Central lab on or prior to Cycle 1 Day 1. In case that a randomized subject was not treated (no Cycle 1 Day 1 date), the date of randomization will be used.

Baseline transferrin saturation will be derived using the serum samples collected at screening. The transferrin saturation result is derived as: iron (umol/L) / total iron binding capacity (umol/L). In case the result of total iron binding capacity is reported as “<xxx”, xxx-1 will be used as the total iron binding capacity to derive the transferrin saturation.

By-subject listings of the baseline disease characteristics will be provided.

In addition to the above baseline disease characteristics, the revised international prognostic scoring system for MDS (IPSS-R, [Greenberg, 2012, Appendix G](#)) will be summarized for exploratory purpose.

IPSS-R score will be classified and summarized as: very low, low, intermediate, high, very high. The derivation for the IPSS-R score is provided in [Appendix G](#). The revised IPSS cytogenetic classification (from central lab) will also be summarized (very good, good, intermediate, poor, very poor).

[REDACTED]

By-subject listings of IPSS-R will be provided.

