16. CHANGES TO THE STATISTICAL ANALYSES SECTION OF THE PROTOCOL

As there were no subjects enrolled from Japanese sites, the randomization stratification factor “country of enrollment (ie, Japan versus ROW)” will not be used when the analysis is performed.

Frequency cross-tabulations of RBC transfusion dependent status for 84 days at baseline versus on treatment will not be provided.

The end date of the evaluation period defined in Section 10.1 is used as the censoring date when calculating the duration of RBC transfusion independence ≥ 56 days and ≥ 84 days, duration of RBC transfusion reduction and duration of platelet transfusion independence. As defined in Section 10.1, the days after a subject started subsequent MDS treatment will not be included in the response duration. The end date of the evaluation period defined in Section 10.1 is also used as the censoring date for subjects who do not achieve the corresponding response during the treatment period in the analysis of time to RBC transfusion independence ≥ 56 days and ≥ 84 days, and time to platelet transfusion independence.

Progression to AML will be identified based on documentations in central lab report or Follow-up Status CRF, please see detail in Section 10.2.8.

No other changes to the statistical analyses section of the protocol are made in this SAP.

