^d In some circumstances, protocol therapy may require the initiation of further treatment (eg, consolidation, maintenance) before the 4-week period. Such subjects can be included in the response category into which they fit at the time the therapy is started. Transient cytopenias during repeated chemotherapy courses should not be considered as interrupting durability of response, as long as they recover to the improved counts of the previous course.

Notes: Subjects with CMML will be assessed for response using the IWG criteria for MDS. Deletions to IWG response criteria are not shown. To convert hemoglobin from grams per deciliter to grams per liter, multiply grams per deciliter by 10.

Source: Cheson BD, Greenberg PL, Bennett JM, Lowenberg B, Wijermans PW, Nimer SD et al. Clinical application and proposal for modification of the International Working Group (IWG) response criteria in myelodysplasia. Blood 2006; 108 (2): 419-25.

Modified Hematologic Improvement According to IWG Criteria	
Hematologic improvement^a	Response criteria (responses must last at least 8 week)^b
Erythroid Response (HI-E) (pretreatment, <11 g/dL)	Hemoglobin increase by ≥ 1.5 g/dL Relevant reduction of units of RBC transfusions by an absolute number of at least 4 RBC transfusions/8 weeks compared with the pretreatment transfusion number in the previous 8 weeks. Only RBC transfusions given for a hemoglobin of ≤ 9.0 g/dL pretreatment will count in the RBC transfusion response evaluation ^b
Platelet Response (HI-P) (pretreatment, <100 X 10 ⁹ /L)	Absolute increase of ≥ 30 X 10 ⁹ /L for subjects starting with > 20 X 10 ⁹ /L platelets Increase from < 20 X 10 ⁹ /L to > 20 X 10 ⁹ /L and by at least 100% ^b
Neutrophil Response (HI-N) (pretreatment, <1.0 X 10 ⁹ /L)	At least 100% increase and an absolute increase > 0.5 X 10 ⁹ /L ^b
Progression or Relapse After HI ^c	At least 1 of the following: At least 50% decrement from maximum response levels in granulocytes or platelets Reduction in hemoglobin by ≥ 1.5 g/dL Transfusion dependence

KEY: HI = hematologic improvement; HI-E = hematologic improvement erythroid response; HI-N = hematologic improvement neutrophil response; HI-P = hematologic improvement platelet response; IWG = International Working Group; MDS = myelodysplastic syndromes; RBC = red blood cell

a Pretreatment counts averages of at least 2 measurements (not influenced by transfusions) ≥ 1 week apart (modification).

b Modification to IWG response criteria.

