c In the absence of another explanation, such as acute infection, repeated courses of chemotherapy (modification), gastrointestinal bleeding, hemolysis, and so forth. It is recommended that the 2 kinds of erythroid and platelet responses be reported overall as well as by the individual response pattern.

Note: Deletions to the IWG response criteria are not shown. To convert hemoglobin levels from grams per deciliter to grams per liter, multiply grams per deciliter by 10.

Source: Cheson BD, Greenberg PL, Bennett JM, Lowenberg B, Wijermans PW, Nimer SD et al. Clinical application and proposal for modification of the International Working Group (IWG) response criteria in myelodysplasia. Blood 2006; 108 (2): 419-25.

18.6. Appendix F: Derivation Rules for Hematologic Response and Hematologic Improvement According to the IWG Criteria for MDS

Following rules will be used to derive the hematologic response, cytogenetic response, and hematologic improvement using central lab data, including [redacted] central lab data for bone marrow. Lab data collected after the date of the end of treatment visit, or last dose date + 28 days, whichever occurs later, will not be used.

In the following derivations, if Hgb or platelet counts are used for evaluation, the Hgb values are only valid to use if there is no RBC/Whole blood transfusion within 7 days prior to the sample collection, the platelet count values are only valid to use if there is no platelet transfusion within 7 days prior to the sample collection.

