18.6.3. Hematologic Improvement

Following rules will be used to derive the hematologic improvement using the central lab data.

- Platelet Response (HI-P):
 - Absolute increase of $\geq 30 \times 10^9/L$ for subjects starting with $> 20 \times 10^9/L$ platelets, or
 - Increase from $\leq 20 \times 10^9/L$ to $> 20 \times 10^9/L$ and by at least 100%.Platelet values within 7 days following a platelet transfusion will not be used.
- Erythroid Response (HI-E):
 - Hgb increase by ≥ 1.5 g/dL, or

- Relevant reduction of units of RBC transfusions by an absolute number of at least 4 RBC transfusions/8 weeks compared with the pretreatment transfusion number in the previous 8 weeks. Only RBC transfusions given for a Hgb of ≤ 10.0 g/dL on treatment will count in the RBC transfusion response evaluation.

Hgb values within 7 days following a RBC/Whole blood transfusion will not be used.

- Neutrophil Response (HI-N) (only derived for subjects with baseline ANC $< 1.0 \times 10^9/L$):
 - At least 100% increase and an absolute increase $> 0.5 \times 10^9/L$.

For HI-E, the relevant reduction of units of RBC transfusions is confirmed by checking whether a subject is a RBC transfusion reduction responder as defined in Section 10.2.11, ie., if the subject has at least 4 units reduction in transfusion units over a consecutive 56 days period compared to the baseline transfusion units in 56 days.

For HI-P, HI-E and HI-N, the above criteria must be met for at least 8 weeks for a subject to be counted as a responder. If a subject doesn't have the subsequent data which meet the response criteria, the subject will not be considered as a responder.

18.7. Appendix G: Revised International Prognostic Scoring System (IPSS-R) for Myelodysplastic Syndromes

The IPSS-R score will be derived per [Greenberg, 2012](#).

Table 2. IPSS-R Prognostic Score Values

Prognostic Variable	0	0.5	1.0	1.5	2.0	3	4
Cytogenetics	Very Good		Good		Intermediate	Poor	Very Poor
Bone Marrow Blast %	≤ 2		>2-<5%		5-10%	>10%	
Hemoglobin (g/dL)	≥10		8-<10	<8			
Platelets (x10 ⁹ /L)	≥100	50-<100	<50				
Absolute Neutrophil Count (x10 ⁹ /L)	≥0.8	<0.8					

Source: Greenberg PL, Tuechler H, Schanz J, Sanz G, Garcia-Manero G, Solé F, et al. Revised International Prognostic Scoring System for Myelodysplastic Syndromes. Blood 2012; 120: 2454-2465.

Table 3. IPSS-R Prognostic Risk Categories/Scores

RISK CATEGORY	RISK SCORE
Very Low	≤ 1.5
Low	> 1.5 – 3
Intermediate	> 3 – 4.5
High	> 4.5 – 6
Very High	> 6

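### SAP baseline hemoglobin for HI-E departs from protocol Appendix D without being declared, and the hemoglobin limb can count a still-transfused subject with no erythroid change as a responder

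*SAP*

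**What the plan says.** **Protocol.** Appendix D, footnote a, reads "Pre-treatment counts averages of at least 2 measurements (not influenced by transfusions, ie, no RBC transfusions for 2 weeks", and asks for measurements at least a week apart. Hemoglobin and platelets get different intervals: "no RBC transfusions for 2 weeks and no platelet transfusions for 1 week". The footnote covers pre-treatment counts only; Appendix D gives no transfusion-free interval for on-treatment hemoglobin. Protocol 10.6.2.2 defines HI-E by Appendix D and presents it descriptively.

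**SAP, baseline.** Section 8.2 works in three steps.
- Step 1: "Use the lowest value among the Hgb values which are collected after >7 days of a RBC/whole blood transfusion", or on the day of a transfusion.
- Step 2, if Step 1 yields nothing: the lowest of the values "which are collected within 7 days after a RBC/whole blood transfusion and within 3 days before another transfusion as the baseline value".
- Step 3: the lowest of all central values up to Cycle 1 Day 1.

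Appendix E keeps the averaging ("Pretreatment counts averages of at least 2 measurements (not influenced by transfusions") but drops the two-week definition.

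**SAP, response.** Section 18.6 states that "the Hgb values are only valid to use if there is no RBC/Whole blood transfusion within 7 days prior to the sample collection", and 18.6.3 repeats it for HI-E: "Hgb values within 7 days following a RBC/Whole blood transfusion will not be used". HI-E is met by a hemoglobin rise of at least 1.5 g/dL or by a reduction of at least 4 RBC units per 8 weeks, held for at least 8 weeks. The hemoglobin limb has no transfusion-free condition.

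**SAP, changes.** Section 16 lists some changes and closes: "No other changes to the statistical analyses section of the protocol are made in this SAP". Neither the baseline window nor the move from average to lowest value is listed.

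**The concern.** Two things meet here. The first is an undeclared change of definition at baseline: one lowest value, which may be a trough on the day of a transfusion, replaces an average of uninfluenced values. The SAP also disagrees with itself, since Appendix E still calls for the average. Section 18.6.3 does not name its baseline; 8.2 is the only derivation the SAP gives.

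The second is a gap on treatment. Subjects entered with no 28-day RBC-transfusion-free stretch in the 56 days before randomization (protocol 7.2), so hemoglobin taken 8 to 14 days after a transfusion should be common. Such a value can still carry transfused cells. Set against a trough baseline, it can show a 1.5 g/dL rise with no change in the marrow.

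False responses of this kind would arise in both arms, dilute the HI-E difference and make the rate depend on local transfusion practice. SAP 10.2.10 compares HI-E between arms as it does HI-P, that is, with the primary endpoint's methods, so the dilution would reach a reported comparison.

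**Working it through.** The plan states no figure to reproduce. The check is whether an unchanged, still-transfused subject can meet the hemoglobin limb, how often, and which rule drives it.

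**Inputs from the documents:** the 1.5 g/dL rise, the 8-week duration, the 7-day validity rule, and central sampling weekly in Cycles 1-2, every two weeks in Cycles 3-12 and monthly thereafter (protocol 6.6.5).

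**Assumptions, not in the documents:** rise of 0.7 to 1.3 g/dL per unit, linear fall back to trough, 2 to 4 units every 14 to 28 days, measurement SD 0.3 or 0.6 g/dL, three central values up to Cycle 1 Day 1, transfusion dates independent of visits.

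**Step 1: residual above trough.** On day d after a transfusion, residual = units × rise per unit × (1 − d/interval). At 1.0 g/dL per unit, on day 8 (the first day valid under the SAP):
- 2 units every 14 days: 2 × (1 − 8/14) = 0.86
- 2 every 21: 2 × (1 − 8/21) = 1.24
- 2 every 28: 2 × (1 − 8/28) = 1.43
- 3 every 21: 3 × (1 − 8/21) = 1.86
- 4 every 28: 4 × (1 − 8/28) = 2.86

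Some patterns clear 1.5 g/dL and others do not. On day 15, 3 every 21 gives 3 × (1 − 15/21) = 0.86, but 4 every 28 still gives 4 × (1 − 15/28) = 1.86. A 14-day window helps but is not a complete cure.

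**Step 2: simulation with fixed transfusion intervals.** 1,500 no-effect subjects per setting; a response means all valid values are at least baseline + 1.5 g/dL over 56 days or more. Percentage scored as HI-E by the hemoglobin limb (SD 0.6 throughout):

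| Pattern (g/dL per unit) | Cycles | SAP rule | Lowest baseline, 14-day on treatment | Average baseline, 7-day on treatment | Average baseline, 14-day on treatment |
|---|---|---|---|---|---|
| 2 units/21 d (1.0) | 12 | 4.3 | 2.5 | 1.8 | 0.5 |
| 3 units/21 d (1.0) | 12 | 5.3 | 2.5 | 2.4 | 0.5 |
| 3 units/21 d (1.0) | about 24 | 14.1 | 4.4 | 7.9 | 2.0 |
| 4 units/28 d (1.3) | 12 | 19.5 | 14.9 | 8.1 | 6.3 |

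Across the whole grid the SAP rule gives 0 to 19.5% over 12 cycles and 0 to 48.8% over about 24; the upper ends come from 4 units every 28 days. The last two columns cover only subjects with two values more than 14 days after a transfusion. That share is about 2-3% at a 14-day interval, 23-28% at 21 days and 49-53% at 28 days. In the 14-day pattern the averaged baseline rests on a few dozen subjects and does not always help: for 3 units at 1.3 g/dL per unit and SD 0.3, it gives 19.5% against 5.5% under the SAP rule.

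**Step 3: simulation with a transfusion trigger.** Assumptions: 2-3 units per episode, 1 g/dL per unit, decline of 0.6-1.3 g/dL per week, SD 0.4, trigger mean 8.0 g/dL. With an unchanged trigger, three runs differing in details such as the number of baseline samples gave 1.5%, 2.9% and 6.6% under the SAP rule. Changing one element at a time in the 1.5% run:
- baseline window 7 to 14 days: 1.5% to 1.2%
- on-treatment window 7 to 14 days: 1.5% to 0.6%
- averaged baseline: 0.0%
- transfusion-free response: 0%

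With the trigger 0.5 g/dL higher on study, the same run gives 8.8% under the SAP rule, 5.0% with 14 days on treatment, 0.7% with averaging and 0% with a transfusion-free response.

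**Step 4: effect on the comparison.** Assume true HI-E of 25% against 10% with 108 per arm (the rates are not in the documents), and let a false rate f turn p into p + f(1 − p). At f = 2.9% the rates become 27.2% and 12.6%. Unpooled SE = √[(0.272 × 0.728 + 0.126 × 0.874)/108] = 0.053, so z = 0.146/0.053 − 1.96 ≈ 0.77 and power is about 78%, against 84% with no false responses.

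**The case against.** The strongest reply is that the two-week rule governs pre-treatment counts only, so SAP 18.6 and 18.6.3 contradict nothing and reasonably fill a gap. That stands. A reader might infer that the SAP breaches Appendix D on treatment, or that replacing 7 by 14 days throughout would merely restore the protocol. Appendix D does not say that.

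It also stands that the baseline window is not the cause. Moving it alone from 7 to 14 days changes almost nothing (1.5% to 1.2%; in another run, 6.6% to 6.2%). The main drivers are the lowest-value baseline and the missing transfusion-free condition, with the on-treatment window a contributor.

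A third tempting reading is a severe loss of power, for example from 84% to 58%. That needs a 13% false rate, which in the run that produced it required a trigger 0.5 g/dL higher on study. No section of either document suggests such a rise.

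There are partial safeguards. The 8-week requirement lets trough values break many runs. SAP 10.2.10 also summarises CRF-recorded HI-E separately. The appendices recommend reporting the two erythroid patterns individually and name transfusion dependence as relapse after improvement, though SAP 18.6.3 turns neither into a rule. Finally, a two-week average is hard to obtain in this population, so a shorter window may be defensible. That is a reason to state and justify the choice, not to leave it undeclared.

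**Conclusion.** The point holds in limited form. The baseline departure from Appendix D is a matter of text: lowest value instead of average, 7 days or fewer instead of two weeks, and no entry in SAP 16. Separately, the hemoglobin limb can score a subject who is still transfused and has no erythroid change.

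With an unchanged trigger over 12 cycles, mid-range settings give about 1 to 5%. Quieter patterns give almost none, one run gave 6.6%, and the heaviest assumed pattern gave 19.5%. Rates rise if the on-study trigger rises or follow-up runs into monthly sampling. All of these rest on assumed transfusion patterns and measurement error.

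A subject who is still transfused may properly be an HI-E responder through the transfusion-reduction limb; only the hemoglobin limb is in question. HI-E is secondary and outside alpha control (SAP 10.2), the rule is the same in both arms, and the primary endpoint and OS are unaffected.

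**What to change.** For the derived HI-E:

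(a) Take baseline hemoglobin as the Appendix D average of at least two uninfluenced values, with a stated fallback. The fallback must cover subjects who have only day 8-14 values. If Step 1 of SAP 8.2 simply moved to 14 days, those values would qualify under neither Step 1 nor Step 2, and the subject would drop to Step 3, which has no washout.

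(b) Require no RBC transfusion during the 8-week hemoglobin-limb response; subjects still transfused remain assessable by the reduction limb. This is the element that closes the gap. If the lowest-value baseline is kept, use a 14-day on-treatment window, at least as a sensitivity analysis.

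(c) List the departure and its reason in SAP 16, and align Appendix E with 8.2.

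The cost is a re-derivation from data already collected: transfusion dates (protocol 6.7.1) and central hemoglobin (6.6.5). The downside is fewer usable hemoglobin values in subjects still being transfused; in one simulation a 14-day rule left about 6 per subject instead of 16. Since the Amendment 6.0 rationale says that the primary report is final, the result should be labelled supplementary.

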18.6.1. Hematologic Response

- **Complete Remission (CR):**

1. At each time point, check if the following criteria are all met:
 - a. Bone marrow blast $\leq 5\%$,
 - b. Peripheral blood blast = 0%,
 - c. Hgb ≥ 11 g/dL,
 - d. Platelets $\geq 100 \times 10^9$ /L,
 - e. Neutrophils $\geq 1.0 \times 10^9$ /L;
2. The criteria in item 1 must be met for at least 4 weeks, ie., within 4 weeks there is no lab result showing any of the criteria (a to e) can't be met. However, if the "4 weeks" assessment/confirmation is not available because the subject discontinued treatment within the 4 weeks following the previous assessment, these records will not contribute to CR.

To derive the responses at each time point, if the bone marrow blast assessment, Hgb, platelet, and/or Neutrophils, are not available, the results obtained from the latest available assessment will be used. For peripheral blood blast, if it is assessed by both [redacted] lab and [redacted] lab at a time point, the higher value will be used; if it is assessed by either [redacted] lab or [redacted] (but not both) at a time point, then the result from the available lab [redacted] lab or [redacted]) will be used; if at a time point, both results are missing, the latest result from either [redacted] lab or [redacted] (but not both) will be used.

CR (Yes) will only be available for subjects with baseline bone marrow blasts $> 5\%$.

- **Partial Remission (PR):**

For PR, all criteria for CR must be met except for 1(a). Replace 1(a) by: Bone marrow blasts decreased by $\geq 50\%$ over pretreatment (baseline value) but still $> 5\%$.

PR (Yes) will only be available for subjects with baseline bone marrow blasts $> 5\%$.

- **Marrow CR (mCR):**

1. At each time point, check if the following criteria are all met:
 - a. Bone marrow $\leq 5\%$;
 - b. Bone marrow reduction from baseline $\geq 50\%$.

2. The criteria in item 1 must be met for at least 2 consecutive bone marrow assessments.

If a subject only has one post-baseline bone marrow result, the subject will not be considered as a responder for mCR.

mCR (Yes) will only be available for subjects with baseline bone marrow blasts > 5%.

- **Disease progression (modified from IWG):**

A subject is considered having disease progress per the following rules:

For patients with:

- < 5% blasts: $\geq 50\%$ increase in blasts and has blasts > 5%
- $\geq 5\%$ - < 10% blasts: $\geq 50\%$ increase and has blasts > 10%
- $\geq 10\%$ - < 20% blasts: $\geq 50\%$ increase and has blasts > 20%
- $\geq 20\%$ - < 30% blasts: $\geq 50\%$ increase and has blasts > 30%

Bone marrow blasts are used.

Or with any of the following:

- a. At least 50% decrement from maximum remission / response levels in neutrophils and $< 1.0 \times 10^9 /L$;
- b. At least 50% decrement from maximum remission / response levels in platelets and $< 100 \times 10^9 /L$;
- c. Reduction from maximum remission / response levels in Hgb by ≥ 2 g/dL and < 11 g/dL;

To confirm a “disease progression”, any of the criteria (a, b and c) a subject met in a previous assessment must be kept for at least 4 weeks.

- **Stable disease:**

For at least 8 weeks, failure to achieve at least mCR, but no evidence of progression.

- **Failure due to death:**

- Death during treatment; AND
- No post-baseline efficacy assessments are available; i.e., no bone marrow or hematology available.

- **Not evaluable:**

- Subject withdrew consent or was lost to follow-up, AND
- Subject was alive at last contact, AND
- No post-baseline efficacy assessments are available; i.e., no bone marrow or hematology available.

- **Relapse after CR or PR:**

A subject is considered having “Relapse after CR or PR” if any of the following is met:

- Return to pretreatment (baseline) bone marrow blast percentage;
- At least 50% decrement from maximum remission / response levels in neutrophils and $< 1.0 \times 10^9 /L$;
- At least 50% decrement from maximum remission / response levels in platelets and $< 100 \times 10^9 /L$;
- Reduction in Hgb concentration from maximum remission / response levels by ≥ 1.5 g/dL and < 11 g/dL or transfusion dependence

To confirm a “relapse”, the criterion a subject met in a previous assessment must be met for at least at least 4 weeks. Subjects will not be evaluable for relapse after CR or PR if no 4 weeks data available.

